7.4.2 Analysis of Secondary Variables

For secondary efficacy endpoints, binary variables such as Percentage of subjects achieving ACR50 response at Week 12/ET, and Percentage of subjects achieving ACR70 response at Week 12/ET will be analyzed (to Week 12/ET) using logistic regression model as described in the primary analysis with treatment group as the factor and the prior biologic-DMARD-IR, concomitant DMARD use during the study period and study region (Japan, Korea and Taiwan) as the covariates. Continuous variables, such as Change from baseline/Day 1 to Week 12/ET in DAS28-CRP and DAS28-ESR scores, will be analyzed using analysis of covariance (ANCOVA) with treatment group as the factor, and the prior biologic-DMARD-IR, concomitant DMARD use, study region (Japan, Korea, and Taiwan), and baseline value as the covariates. Each ASP015K group will be compared with placebo group (to Week 12/ET) and multiplicity for the secondary efficacy variables will not be adjusted.

7.5 Analysis of Safety

The following analyses will be performed on SAF. Unless otherwise noted, analysis will be performed for the treatment groups at allocation (ASP015K 100 mg, ASP015K 150 mg, placebo, reference groups) and, if necessary, for the treatment groups after placebo was

- CONFIDENTIAL -

switched to active treatment (ASP015K 100 mg, ASP015K 150 mg, placebo–ASP015K 100 mg, placebo–ASP015K 150 mg, reference groups). In addition, analysis will be performed for each study region (Japan, Korea, and Taiwan).

7.5.1 Adverse Events

AEs will be coded using the Medical Dictionary for Regulatory Activities (MedDRA/J). The incidence of AEs, SAEs, AEs leading to discontinuation, and AEs whose relationship to study drugs or reference drugs could not be ruled out will be summarized by system organ class and preferred term, as well as the treatment group. The incidence of AEs by severity will also be summarized.

7.5.2 Laboratory Assessments

Descriptive statistics will be used to summarize clinical laboratory measurements and the change from baseline if quantitative, by time point.

7.5.3 Vital Signs

Descriptive statistics will be used to summarize vital sign measurements and the change from baseline by time point.

7.5.4 12-lead ECG

The frequency of each category of 12-lead ECG results will be summarized by time point.

7.5.5 QT assessment

Descriptive statistics will be used to summarize QT assessment (including QTc assessment) measurements and the change from baseline.

The frequency of each category of QT assessment (including QTc assessment) will be summarized by time point.

In addition, the relationship between quantity of QT change and concentration of ASP015K may be explored.

7.5.6 Body Weight

Descriptive statistics will be used to summarize measurements by time point.

7.6 Analysis of Pharmacokinetics

A detailed elaboration of the PK analysis will be included in a separate PK analysis plan. The trough plasma concentrations of ASP015K will be summarized by treatment group and visit. In addition, the same PK analysis will be conducted for each study region (Japan, Korea, and Taiwan). Exploratory population PK analysis may be performed by pooling the results obtained so far.

- CONFIDENTIAL -

7.7 Other Analyses

7.7.1 Analysis of Pharmacodynamics

Analysis will be performed in PDAS. Descriptive statistics will be used to summarize PD measurements and the change from baseline by time point.

7.7.2 Analysis of Pharmacogenomics

At present, the content of analysis as part of pharmacogenomic research has not been determined yet. The relationship between the results from genetic analyses and study data (clinical information such as pharmacological activity, toxicity and PK) may be explored in the future. The sponsor can initiate such research once a specific methodology is established. Prior to research, the sponsor will prepare a research plan (including procedures and timing of document disposal) and have appropriateness of conduct of the research reviewed and approved by the sponsor's ethics review committee from ethical and scientific viewpoints.

7.8 Interim Analysis (and Early Discontinuation of the Clinical Study)

Not applicable. Review of safety data and safety evaluation will be completed by an independent DSMB [see Section 10.1 Independent Data and Safety Monitoring Board (DSMB)] during the study in accordance with separate SOP.

7.9 Handling of Missing Data, Outliers, Visit Windows, and Other Information

Final judgments on handling of missing data, outliers, visit windows, and other information will be made at the Case Review Meeting based on the opinions and advice from a medical expert and/or statistical advisor prior to treatment code breaking and included in the SAP.

The acceptable time ranges for the efficacy and safety examinations and observations from the date of initial study or reference treatment (Day 1) are defined as follows. If there are multiple data available over the same period of time, the data obtained on the date closest to the reference date will be utilized; the later date will be applied if the number of days from the reference date is equal. Subjects who have no evaluable post-dose data on ACR20, ACR50, and ACR70 response rates after initial treatment with the study drug or reference drug will be counted as non-responders and included in the analysis at the end of Week 12 (Week 12 or at early termination before Week 12).

7.9.1 Handling of Schedule of Assessments of Efficacy Variables

For data after the end of study treatment, data obtained within + 2 days after the last dose is taken will be included in analysis. For data after the end of reference treatment, data obtained within + 9 days after the last dose will be included in analysis.

- CONFIDENTIAL -

(1) TJC (68 joints)/SJC (66 joints), laboratory test (CRP)

Time points defined in analysis	Reference date*	Acceptable time range
Screening	Day -28 to Day -1	Day -28 to Day -1
Baseline	Day 1	Day 1
Week 4 to Week 48**	Day $7 \times x + 1$	Day $(7 \times x - 6)$ to Day $(7 \times x + 8)$ and before the initiation of treatment with the study drug or reference drug on the visit day
Week 52	Day 365	Day 358 to Day 372
End of Week 12 (Week 12 or at early termination before Week 12)	Day 85	Day 2 to Day 92
End of treatment (Week 52 or at early termination)	Day 365	Day 2 to Day 372

*: Day 1 represents the first day of study or reference treatment. The day before the initiation of treatment with the study drug or reference drug is expressed as Day -1.

** : Represents the reference date and acceptable time range for Week x.

(2) PGA and SGA (VAS), subject's assessment of pain (VAS), HAQ-DI, laboratory test (ESR)

Time points defined in analysis	Reference date*	Acceptable time range
Baseline	Day 1	Day 1
Week 4 to Week 48**	Day $7 \times x + 1$	Day $(7 \times x - 6)$ to Day $(7 \times x + 8)$ and before the initiation of treatment with the study drug or reference drug on the visit day
Week 52	Day 365	Day 358 to Day 372
End of Week 12 (Week 12 or at early termination before Week 12)	Day 85	Day 2 to Day 92
End of treatment (Week 52 or at early termination)	Day 365	Day 2 to Day 372

*: Day 1 represents the first day of study or reference treatment. The day before the initiation of treatment with the study drug or reference drug is expressed as Day -1.

** : Represents the reference date and acceptable time range for Week x.

(3) SF-36 v2[®], WPAI

Time points defined in analysis	Reference date*	Acceptable time range
Baseline	Day 1	Day 1
Week 4 to Week 28**	Day $7 \times x + 1$	Day $(7 \times x - 6)$ to Day $(7 \times x + 8)$ and before the initiation of treatment with the study drug or reference drug on the visit day
Week 52	Day 365	Day 358 to Day 372
End of Week 12 (Week 12 or at early termination before Week 12)	Day 85	Day 2 to Day 92
End of treatment (Week 52 or at early termination)	Day 365	Day 2 to Day 372

*: Day 1 represents the first day of study or reference treatment. The day before the initiation of treatment with the study drug or reference drug is expressed as Day -1.

** : Represents the reference date and acceptable time range for Week x.

7.9.2 Handling of Schedule of Assessments of Safety Variables

For data obtained after the end of study treatment, the data obtained within + 2 days after the last dose is taken will be included in analysis. For data after the end of reference treatment, data obtained within + 9 days after the last dose will be included in analysis.

- CONFIDENTIAL -

(1) Physical examination, vital signs, laboratory test [hematology, biochemistry, urinalysis, and pregnancy test (serum and urine)]

Time points defined in analysis	Reference date*	Acceptable time range
Screening	Day -28 to Day -1	Day -28 to Day -1
Baseline	Day 1	Day 1
Week 4 to Week 48**	Day $7 \times x + 1$	Day $(7 \times x - 6)$ to Day $(7 \times x + 8)$ and before the initiation of treatment with the study drug or reference drug on the visit day
Week 52	Day 365	Day 358 to Day 372
End of Week 12 (Week 12 or at early termination before Week 12)	Day 85	Day 2 to Day 92
End of treatment (Week 52 or at early termination)	Day 365	Day 2 to Day 372

*: Day 1 represents the first day of study or reference treatment. The day before the initiation of treatment with the study drug or reference drug is expressed as Day -1.

** : Represents the reference date and acceptable time range for Week x.

(2) Laboratory test (fasting lipid profile test)

Time points defined in analysis	Reference date*	Acceptable time range
Baseline	Day 1	Before the initiation of treatment with the study drug or reference drug on Day 1 and at least 8 hours after the last meal
Week 12	Day 85	Day 78 to Day 92
Week 28	Day 197	Day 190 to Day 204
Week 40	Day 281	Day 274 to Day 288
Week 52	Day 365	Day 358 to Day 372
End of Week 12 (Week 12 or at early termination before Week 12)	Day 85	Day 2 to Day 92
End of treatment (Week 52 or at early termination)	Day 365	Day 2 to Day 372

*: Day 1 represents the first day of study or reference treatment. The day before the initiation of treatment with the study drug or reference drug is expressed as Day -1.

(3) 12-lead ECG

Time points defined in analysis	Reference date*	Acceptable time range
Screening	Day -28 to Day -1	Day -28 to Day -1
Week 28	Day 197	Day 190 to Day 204
Week 52	Day 365	Day 358 to Day 372
End of treatment (Week 52 or at early termination)	Day 365	Day 2 to Day 372

*: Day 1 represents the first day of study or reference treatment. The day before the initiation of treatment with the study drug or reference drug is expressed as Day -1.

- CONFIDENTIAL -

(4) Body weight

Time points defined in analysis	Reference date*	Acceptable time range
Screening	Day -28 to Day -1	Day -28 to Day -1
Week 12	Day 85	Day 78 to Day 92
Week 28	Day 197	Day 190 to Day 204
Week 40	Day 281	Day 274 to Day 288
Week 52	Day 365	Day 358 to Day 372
End of Week 12 (Week 12 or at early termination before Week 12)	Day 85	Day 2 to Day 92
End of treatment (Week 52 or at early termination)	Day 365	Day 2 to Day 372

*: Day 1 represents the first day of study or reference treatment. The day before the initiation of treatment with the study drug or reference drug is expressed as Day -1.

(5) QT assessment (except the reference group)

Time points defined in analysis	Reference date*	Acceptable time range
Baseline	Day 1	Day 1 Before the initiation of treatment with the study drug
Week 4 or 8 (before study drug administration)	Day 29 or Day 57	Before the initiation of treatment with the study drug on Reference date ± 7
Week 4 or 8 (after study drug administration)	Day 29 or Day 57	2 hours post-dose (reference time, but within the range of 1 hour to 4 hours post-dose is acceptable) on Reference date ± 7

7.9.3 Handling of Schedule of Assessments of Pharmacodynamic Variables

For data obtained after the end of study treatment, data obtained within + 2 days after the last dose will be included in analysis. For data after the end of reference treatment, data obtained within + 9 days after the last dose will be included in analysis.

(1) Biomarkers and lymphocyte subsets

Time points defined in analysis	Reference date*	Acceptable time range
Baseline	Day 1	Before the initiation of treatment with the study drug or reference drug on Day 1
Week 4 to Week 28**	Day $7 \times x + 1$	Day $(7 \times x - 6)$ to Day $(7 \times x + 8)$ and before the initiation of treatment with the study drug or reference drug on the visit day
Week 52	Day 365	Day 358 to Day 372
End of Week 12 (Week 12 or at early termination before Week 12)	Day 85	Day 2 to Day 92
End of treatment (Week 52 or at early termination)	Day 365	Day 2 to Day 372

*: Day 1 represents the first day of study or reference treatment.

** : Represents the reference date and acceptable time range for Week x.

- CONFIDENTIAL -

7.9.4 Handling of Schedule of Assessments of Pharmacokinetic Variables**(1) Trough concentration (except the reference group)**

Time points defined in analysis	Reference date*	Acceptable time range
Baseline	Day 1	Before the initiation of treatment with the study drug on Day 1
Weeks 4, 8, 12, 28, and 52**	Day $7 \times x + 1$	Day $(7 \times x - 6)$ to Day $(7 \times x + 8)$ and within 19 to 29 hours between the time of treatment with the study drug before blood collection and the time of blood collection

*: Day 1 represents the first day of study treatment.

**: Represents the reference date and acceptable time range for Week x.

(2) Post-dose concentration (except the reference group)

Time points defined in analysis	Reference date*	Acceptable time range
Week 4 or Week 8**	Day $7 \times x + 1$	Day $(7 \times x - 6)$ to Day $(7 \times x + 8)$ and within 1 to 4 hours between the time of treatment with the study drug before blood collection and the time of blood collection

*: Day 1 represents the first day of study treatment.

**: Represents the reference date and acceptable time range for Week x.

- CONFIDENTIAL -

8 OPERATIONAL AND ADMINISTRATIVE CONSIDERATIONS

8.1 Procedure for Clinical Study Quality Control

8.1.1 Data Collection

The investigator is responsible to ensure that all data in the eCRFs and queries are accurate and complete and that all entries are verifiable with source documents. These source documents should be appropriately maintained by the study center.

The investigator, sub-investigator, or collaborator will enter data collected using an Electronic Data Capture (EDC) system. The investigator, sub-investigator, or collaborator will enter the data, in principle within 5 working days from the creation of the data (date of visit by the subject, date of obtaining information, etc.).

In principle, the name of AE must be entered within 5 working days of the date of confirming its occurrence. The name of concomitant drug/therapy must also be entered within 5 working days of the awareness of its use. Other information to be entered in the eCRF must be entered immediately on receipt.

The monitor should verify the data in the eCRFs with source documents and confirm that there are no inconsistencies between them.

For screening failures, the minimum demographic data (sex, birth date, study region, and informed consent date) and, if reason for screening failure is to be obtained, the screening failure log (SFL) will be collected.

Measurements of laboratory tests, pharmacodynamic parameters, and plasma drug concentrations will be performed by central laboratory. The Data Science Department of the sponsor will obtain the laboratory test results, pharmacodynamic measurements, and plasma drug concentration measurements in an electronic format from central laboratory at predefined intervals during the study.

Analysis of Central ECG will be performed by [REDACTED] The Data Science Department of the sponsor will obtain the quality assured analysis data in an electronic format from [REDACTED] at predefined timing.

The central laboratory and [REDACTED] will provide the sponsor with a copy of the complete and clean data, together with the quality control report.

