5.3.2 Pharmacodynamic Assessments

Blood samples will be collected at baseline and on days specified in the Schedule of Assessments. At the study visit points where blood sample collection for PK assessment is performed, sample collection for PD assessment will be performed before treatment with the study drug or reference drug and at the same time as that for the sampling for PK assessment. These measurements will be performed at the central laboratory, and the results will be reported to the sponsor and the study center after the breaking of the treatment code.

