5.6 Test Drug Concentration

The plasma concentrations of ASP015K will be measured in the samples collected at the time points in Table 1 Schedule of Assessments, except the reference group. The concentrations of ASP015K metabolites H1, H2, and H4 will also be measured if necessary.

In the placebo group, the concentrations of samples collected during the period of the administration of placebo will not be measured, but the concentration of samples collected after switching to ASP015K 100 mg or ASP015K 150 mg will be measured. The concentration of the sample collected on the day of the visit for switching will be measured as baseline.

- CONFIDENTIAL -

The subject registration center will provide information on study drug assignment to the institution performing measurements of drug concentrations. The institution performing measurements of drug concentrations will measure the drug concentrations of samples of subjects in the placebo group who switched to ASP015K 100 mg or ASP015K 150 mg.

Concentration measurements will be performed by central laboratory using a validated, established LC-MS/MS method [Test No.: ██████████ (ASP015K, H2), ██████████ (H4), ██████████ (H1)]. The lower limit of quantification is 0.25 ng/mL. Blood samples for drug concentration (2 mL/sample) will be collected into a 2 mL vacutainer tube containing ethylenediamine-tetra-acetic acid (K₃EDTA-3K). See the written explanation of testing procedure enclosed in the clinical laboratory testing kit for descriptions of the procedure for sampling blood and storing and shipping the blood samples. The central laboratory will not report the results of determinations to the investigator, sub-investigator, sponsor, or other third parties until the breaking of the treatment code.

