5.7 Other Measurements, Assessments, or Methods

5.7.1 Pharmacodynamic Measurements

In this study, the following will be measured as part of the pharmacodynamic evaluation: biomarkers of bone or cartilage metabolism and lymphocyte subsets (see Section 5.3.2.2 Biomarkers for Efficacy and Safety Assessments).

Blood samples for biomarkers of bone or cartilage metabolism will be collected in a 2 mL sampling tube containing EDTA-2Na, and samples for lymphocyte subsets will be collected in a 2 mL vacutainer tube containing EDTA-2K in Japan, and in a 3 mL vacutainer tube containing EDTA-2K in Korea and Taiwan. See the written explanation of testing procedure enclosed in the clinical laboratory testing kit for descriptions of the procedure for sampling blood and storing and shipping the blood samples.

The central laboratory will not report the results to the investigator, sub-investigator, sponsor, or other third parties until the breaking of the treatment code.

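### Protocol 8.1.1 sends PK and PD results to sponsor data management during the study, against 5.6, 5.7.1 and 5.3.2; followed as written and unmasked, the PK file would separate placebo from ASP015K

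*Protocol*

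**What the plan says.** Protocol 8.1.1 (Data Collection) puts three kinds of central-laboratory data into one transfer rule. The sponsor's Data Science Department is to obtain laboratory test results, "pharmacodynamic measurements, and plasma drug concentration measurements in an electronic format from central laboratory at predefined intervals during the study". Section 8.1.5 gives the same department the coordination of data management.

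Three other sections hold back the PK and PD part of that data:

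- **PK, Section 5.6:** the laboratory that runs the assays "will not report the results of determinations to the investigator, sub-investigator, sponsor, or other third parties until the breaking of the treatment code".
- **PD, Section 5.7.1:** "The central laboratory will not report the results to the investigator, sub-investigator, sponsor, or other third parties until the breaking of the treatment code".
- **PD, Section 5.3.2:** "the results will be reported to the sponsor and the study center after the breaking of the treatment code".

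Section 5.6 also sets out what is assayed in the placebo arm: "In the placebo group, the concentrations of samples collected during the period of the administration of placebo will not be measured". Samples after the switch to ASP015K are measured, and for the switch visit itself: "The concentration of the sample collected on the day of the visit for switching will be measured as baseline". On the assay: "The lower limit of quantification is 0.25 ng/mL".

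Section 4.4.1 restricts knowledge of the treatment code to the person who assigns study drugs, an appointed person at the institution measuring concentrations, Safety Control staff when a SUSAR requires it, and the DSMB.

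**The concern.** The same results are to reach the sponsor at intervals during the study under one section and only after code breaking under three others. Anyone drawing up the laboratory transfer agreement has to breach one rule or the other.

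For PK the choice affects the blind. The laboratory works from the assignment information (4.4.3, 5.6) and skips samples taken on placebo. Whether a result exists therefore depends on the arm, and a reader of the file could infer treatment from which rows are present.

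At stake are decisions that the plan intends to be made blind. Missing data, outliers and visit windows are settled at the Case Review Meeting before code breaking (Protocol 7.9). Inclusion in and exclusion from the analyses are settled at the Case Review (7.2), where subjects who fail PPS criteria may be readmitted on judgment (7.2.2). The SAP is to be signed before unblinding (SAP 1).

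**Working it through.** No formula applies. The check compares the release rules, then asks what the PK file would contain.

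**1. Can the rules be reconciled?**

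- *Reading 8.1.1 as delivery at study end.* It specifies intervals during the study, and a separate sentence in the same section covers delivery of the complete, clean data with the quality control report.
- *Reading the intervals as applying only to routine laboratory tests.* The sentence names PD and plasma concentration measurements explicitly and gives all three the same timing.
- *Code breaking during the study.* The SAP is signed before unblinding. Versions 2.00 and 2.10 are dated 19-Jan-2018 (SAP 8), after the planned study end of December 2017 (Protocol synopsis).

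None of these removes the conflict.

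**2. What would an unmasked PK file show?**

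Trough samples are scheduled at baseline, Weeks 4, 8, 12, 28 and 52, and early termination, in all arms except etanercept. Applying the assay rule in 5.6 to the post-baseline scheduled visits gives:

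| Arm | Week 4 | Week 8 | Week 12 | Weeks 28, 52 |
|---|---|---|---|---|
| ASP015K 100 mg, 150 mg | result | result | result | result |
| Placebo, then ASP015K | not assayed | not assayed | result, expected below 0.25 ng/mL | result |

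Weeks 4 and 8 separate the arms by whether a result is present, whatever the concentration. Assaying the placebo arm's switch-visit sample does not restore the blind. That sample is drawn before the first ASP015K dose, so it should be below the quantification limit. Separation at Week 12 assumes that ASP015K troughs are quantifiable; separation at Weeks 4 and 8 does not.

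**3. How many subjects?**

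The planned blinded arms hold 100 + 100 + 100 = 300 subjects: 100 on placebo (one third) and 200 on ASP015K. A footnote to the blood-volume table in 5.8 could be read as excluding Taiwan from PK sampling, but the volumes say otherwise:

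- Baseline, Taiwan: 16.5 + 2 (trough) + 8.5 = 27 mL, as stated.
- Total, Taiwan: 264 + 5 + 5 + 12 (trough) + 59.5 + 2 (post-dose) = 347.5 mL, as stated. Without the 14 mL of PK blood it is 333.5 mL, the stated figure for the Taiwan reference group.

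Taiwan subjects in the blinded arms are therefore counted here.

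**4. Do PD results identify the arm?**

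No selective-assay rule applies to VEGF, MMP-3 or lymphocyte subsets. The PD conflict is one of text only.

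**5. Is the recipient allowed to know?**

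Data Science is not on the list in 4.4.1. Neither 8.1.1 nor 8.1.5 mentions masked identifiers, dummy values or a separate unblinded team.

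**The case against.** The strongest reply is that the protocol's intent is plain. Three specific sections withhold the results and one general data-handling sentence says otherwise, so a sensible sponsor would follow the specific sections. File format, transfer dates and access limits belong to data-management documents that are not available here, and those may already mask the data. This stands as far as it goes: the documents permit an unblinding transfer, but they do not show that one took place.

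Some stronger conclusions that a reader might draw are not supported:

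- *That every placebo subject is identified.* A subject who leaves before any on-treatment sample cannot be classified, and an ASP015K subject who misses Weeks 4 and 8 looks like placebo until a later result arrives.
- *That the Case Review, PPS or SAP decisions are no longer blind.* No section says that Data Science staff take them. SAP 1 has the analysis coordinated by a biostatistician, and Protocol 7.2 and 7.9 place the judgments at the Case Review on medical or statistical advice without giving its membership.
- *That the primary comparison is compromised.* The FAS definition, model, test order and LOCF rule are fixed in Protocol 7.2.1 and 7.4.1.1, and SAP 7.11.3 keeps all values. Joint counts and global assessments come from investigators and subjects, who do not receive this transfer. The remaining discretion lies mainly in PPS membership and residual Case Review judgments.

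The reply does not remove the contradiction itself. No section says which rule prevails.

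**Conclusion.** The point holds as an internal contradiction with a conditional consequence. Section 8.1.1 conflicts with 5.6 on PK and with 5.7.1 and 5.3.2 on PD.

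If 8.1.1 were followed as written with unmasked subject-level data, the PK file would separate placebo from ASP015K among subjects with on-treatment samples: up to about 100 against about 200 of the 300 planned in the blinded arms. The presence of results does not by itself tell 100 mg from 150 mg. The open-label etanercept arm is unaffected.

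The conclusion assumes that results are sent subject by subject, under real identifiers, before code breaking. The duration of any exposure cannot be stated, because the transfer dates are not given. An actual break of the blind is not shown. The correction is still warranted: the text as it stands directs treatment-revealing data to a department outside the list in 4.4.1, with no stated safeguard, while decisions meant to precede code breaking are still open.

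**What to change.** Amend 8.1.1 so that electronic transfers during the study cover routine safety laboratory data only, and state that PK and PD results go to the sponsor after code breaking, as 5.6, 5.7.1 and 5.3.2 already require. Appendix 2 collects MMP-3 within the biochemistry samples, so the laboratory transfer specification should exclude it by name.

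If earlier transfer is needed for reconciliation, specify instead a masked transfer (scrambled identifiers or dummy values), or a firewalled recipient added to the list in 4.4.1, and align 5.6, 5.7.1 and 5.3.2 with it. Masking must also hide which samples have no result, since their absence is what identifies placebo.

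The first option costs one sentence and a change to the transfer agreement, and moves PK and PD reconciliation to after code breaking. The second keeps earlier reconciliation at the cost of setting up and documenting the masked or firewalled route.
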